10.5. Appendix 5: Protocol Amendment History

This is an original protocol.

It is recognized that the Coronavirus Disease 2019 (COVID-19) pandemic may have an impact on the conduct of this clinical study due to, for example, self-isolation/quarantine by participants and study-site personnel; travel restrictions/limited access to public places, including hospitals; study site personnel being reassigned to critical tasks.

In alignment with recent health authority guidance, the sponsor is providing options for study related participant management in the event of disruption to the conduct of the study. This guidance does not supersede any local or government requirements or the clinical judgement of the investigator to protect the health and well-being of participants and site staff. If, at any time, a participant's safety is considered to be at risk, study intervention will be discontinued, and study follow-up will be conducted.

Scheduled visits that cannot be conducted in person at the study site will be performed to the extent possible remotely/virtually or delayed until such time that on-site visits can be resumed. At each contact, participants will be interviewed to collect safety data. Key immunogenicity endpoint assessments should be performed if required and as feasible. Participants will also be questioned regarding general health status to fulfill any physical examination requirement.

Every effort should be made to adhere to protocol-specified assessments for participants on study intervention, including follow up. Modifications to protocol-required assessments may be permitted via COVID-19 Appendix after consultation with the participant, investigator, and the sponsor. Missed assessments/visits will be captured in the clinical trial management system for protocol deviations. Discontinuations of study interventions and withdrawal from the study should be documented with the prefix "COVID-19-related" in the case report form (CRF).

The sponsor will continue to monitor the conduct and progress of the clinical study, and any changes will be communicated to the sites and to the health authorities according to local guidance. If a participant has tested positive for COVID-19, the investigator should contact the sponsor's responsible medical officer to discuss plans for study intervention and follow-up. Modifications made to the study conduct as a result of the COVID-19 pandemic should be summarized in the clinical study report.

GUIDANCE SPECIFIC TO THIS PROTOCOL:

Screening and Randomization

- Enrollment of new participants may continue based on the investigator's assessment of risks versus benefits, depending on the situation at a particular site, and the ability to monitor participant safety.
- Baseline visits for participants recently screened for this study should be postponed if the current situation does not allow for an orderly conduct of the study.

Site Visits

- When site visits are not possible due to local/national guidelines, sites should collect the assessments via telephone visits or home-based visits, if the participant allows. The actual visit date and the type of visit (ie, telephone or home-based visit) should be captured in the eCRF according to the eCRF completion guidelines. Procedures that cannot be performed during a home-based visit (eg, clinical assessments, blood samples, nasal samples and physical examination), should be excluded.

Vaccine Administration

- When planning for vaccination visits, local/national or institutional guidelines will be followed. The study vaccine must be administered by an (unblinded) pharmacist or other qualified individual at the study site. If this is not possible, a solution may be considered in consultation with the sponsor and taking into consideration participant safety.

Informed Consent Form

- Consenting and re-consenting of participants for the measures taken (including also remote consenting by phone or video consultation) will be performed as applicable and according to local guidance for informed consent applicable during the COVID-19 pandemic. The process is to be documented in the source documents.

Source Data Verification/Monitoring

- In case on-site monitoring visits are not be possible, the site monitor may contact the investigator to arrange monitoring visits and activities remotely (in accordance with site and local requirements). Additional on-site monitoring visits may be needed in the future to catch up on source data verification.

Site Audits

- During the COVID-19 pandemic and at the impacted sites, study site GCP audits with direct impact/engagement from the investigator and study site personnel would not be conducted in order to comply with national, local, and/or organizational social distancing restrictions. Additional quality assurance activities such as remote audits or focused review of study related documents may take place with limited impact/engagement if possible.

INVESTIGATOR AGREEMENT

COVID-19 Appendix
VAC18193 (JNJ-64400141/JNJ-64213175)

**AMENDMENT HISTORY**

SAP History VAC18193RSV2005			
Document Type and File Name	Issue Date	Amendment Type	Comments
Initial Statistical Analysis Plan VAC18193RSV2005 SAP	09-June-2020	-	-

## ABBREVIATIONS

Ad26	adenovirus serotype 26
ADaM	analysis data model
AE	adverse event
BMI	body mass index
CD	cluster of differentiation
CI	confidence interval
CTP	clinical trial protocol
DPS	data presentation specifications
DRC	data review committee
ELISA	enzyme-linked immunospot
ELISpot	enzyme-linked immunosorbent assay
FA	full analysis (analysis set)
F protein	fusion protein
FDA	Food and Drug Administration
GMT	geometric mean titer
ICS	intracellular cytokine staining
IFN $\gamma$	interferon gamma
Ig	immunoglobulin
IL	interleukin
LLOQ	lower limit of quantification
MedDRA	Medical Dictionary for Regulatory Activities
PPI	per-protocol immunogenicity (analysis set)
pre-F	pre-fusion
RSV	respiratory syncytial virus
SAE	serious adverse event
SAP	Statistical Analysis Plan
SD	standard deviation
SDTM	standard data tabulation model
SE	standard error
Th	T-helper (cell)
TNF $\alpha$	tumor necrosis factor alpha
ULOQ	upper limit of quantification
VNA	virus neutralization assay
vp	viral particles
WHO	World Health Organization

## 1. INTRODUCTION

This statistical analysis plan (SAP) contains information needed to perform the complete safety and immunogenicity analysis of the VAC18193RSV2005 trial. It applies to the primary and final analyses, as specified below:

- Cohort 1 primary analysis will include 14-day immunogenicity and 28-day safety data of all groups in Cohort 1. The sponsor will be unblinded for Cohort 1 at the time of the primary analysis of Cohort 1, and the blind will be maintained at the participant and study site level up to study end.
- Cohort 2 and 3 primary analysis will include 28-day safety data of all groups in Cohorts 2 and 3. If 14-day immunogenicity data are available at the time of the primary analysis, these will be included as well, otherwise these will be analyzed at a later timepoint. The sponsor will be unblinded for Cohorts 2 and 3 at the time of the primary analysis, and the blind will be maintained at the participant and study site level up to study end.
- Final analysis at the end of the study will include safety and immunogenicity data from all cohorts. Data collected up to the time of the last visit for the last participant will be included in the analysis. This analysis will be performed on unblinded data.

Note: The final analysis might be done per cohort, depending on the timing.

This document is based on the clinical trial protocol (CTP) version 2.0 (EDMS-ERI-201635401). The specifications of individual tables, listings and figures to be generated in each analysis will be described in a separate data presentation specifications (DPS) document.

### 1.1. Study Objectives

Refer to Section 3 of the CTP.

### 1.2. Study Design

Refer to Section 4 of the CTP.

### 1.3. Statistical Hypotheses for Study Objectives

No formal statistical testing is planned. The data will be analyzed descriptively.

### 1.4. Sample Size Justification

Refer to Section 9.2 of the CTP.

### 1.5. Randomization and Blinding

Refer to Section 6.3 of the CTP.

### 1.6. Changes to Planned Analysis

No changes from the planned analysis have been determined.

## 2. GENERAL ANALYSIS DEFINITIONS

### 2.1. Study Phases

A baseline (or reference) value will be defined as the value of the last available assessment prior to the vaccination on Day 1.

Study day or relative day is defined as follows:

- Study Day = visit date – date of Day 1 + 1; if visit date  $\geq$  date of Day 1 (date of first vaccination).
- Study Day = visit date – date of Day 1; if visit date  $<$  date of Day 1 (date of first vaccination).

#### 2.1.1. Phase Definitions

The phases in the study will be constructed as follows for the first year/season:

**Table 1: Definitions of the Analysis Phases**

Phase	Phase	Period	Period	Interval	
				From	To
Screening	1			Date and time of signing the informed consent form	One minute prior to start of post dose period
Regimen	2	Post-dose	1	Date and time of first vaccination	
Minimum of:
 
 
a) 23:59 at the date of last contact (for early discontinuation from study)
 
b) 23:59 at the date of database cut-off date for interim analyses
 
c) Maximum (28 days after first vaccination at 23:59, scheduled visit 4 weeks after first vaccination at 23:59)
 

Follow-up	3			One minute after the end of the post-dose period	
Minimum of:
 
 
a) 23:59 at the date of last contact
 
b) 23:59 at the date of database cut-off date for interim analyses
 

Adverse events and concomitant medications will be allocated to the above phases and period, see details in Section 6.1 and Section 4.4 respectively. The regimen phase (post-dose period) is considered the active phase, the screening and follow-up phase are considered non-active phases.

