- g. Systolic and diastolic blood pressure (supine) and heart and respiratory rate measurements should be preceded by at least 5 minutes of rest in a quiet setting without distractions (eg, television, cell phones). Vital signs measurements should be taken before nasal sampling and blood draws, if applicable.
- h. To review inclusion criterion 3 and exclusion criteria 2, 8, 9, 10, 11, and 12.
- i. Investigator must check for acute illness or body temperature of $\geq 38.0^{\circ}\text{C}$ ($\geq 100.4^{\circ}\text{F}$) at the time of vaccination. In such cases, the participant may be vaccinated up to, and no later than, 10 days after the scheduled vaccination, or be withdrawn from vaccination at the discretion of the investigator.
- j. After vaccination, participants will be closely observed for a minimum of 30 minutes to monitor for the development of any acute reactions and solicited events, or longer if deemed necessary by the investigator. Any unsolicited and solicited local (injection site) or systemic AEs, and vital signs (heart and respiratory rate, systolic and diastolic blood pressure [supine], and body temperature) will be documented by the study-site personnel following this observation period.
- k. Participants will be asked to note in the participant diary occurrences of injection site pain/tenderness, erythema, and swelling at the injection site daily. The extent (largest diameter) of any erythema and swelling should be measured using the supplied ruler and recorded daily. Body temperature (oral route preferred) should be measured at approximately the same time each day, preferably in the evening, using the supplied thermometer. If more than one measurement is made on any given day, the highest body temperature of that day will be used in the participant diary.
- l. AEs and special reporting situations related to study procedures or to noninvestigational sponsor products will be reported from the time a signed and dated ICF is obtained until the end of the study/early withdrawal. All other AEs (unsolicited) and other special reporting situations will be reported from the time of vaccination until 28 days after vaccination. All AEs leading to discontinuation of study vaccination (regardless of the causal relationship) are to be reported from the moment of vaccination until completion of the participant's last study-related procedure, which may include contact for safety follow-up.

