3. OBJECTIVES AND ENDPOINTS

Objectives	Endpoints
Cohort 1	
Primary	

 To explore the dose-response relationship of humoral immune responses induced by different dose levels of the Ad26.RSV.preF-based vaccine 	
 Antibody titers to RSV preF protein using preF enzyme-linked immunosorbent assay (ELISA) at 14 days after vaccination
Secondary	

 To explore the dose-response relationship of humoral and cellular immune responses induced by different dose levels of the Ad26.RSV.preF-based vaccine 	
 Antibody titers to RSV preF protein using preF ELISA at 3 and 6 months after vaccination RSV A2 neutralizing antibody levels at 14 days and 3 and 6 months after vaccination IFN-γ ELISpot assay at 14 days and 3 and 6 months after vaccination

 To assess the safety and reactogenicity of different dose levels of the Ad26.RSV.preF-based vaccine 	
 SAEs from the time of vaccination until the end of the study Solicited local and systemic AEs from the time of vaccination until 7 days after vaccination Unsolicited AEs from the time of vaccination until 28 days after vaccination
Exploratory	

 To explore additional vaccine-elicited immune responses 	
Assays that may be used include, but are not limited to:
 
 Post-F protein binding antibodies (ELISA) Antigen-specific T-cell immune responses RSV cross-neutralization of B and/or other A strain(s) Anti-F protein antibody specificity characterization Analysis of immunoglobulin (Ig)A and/or IgG antibodies binding to RSV F protein in prefusion and/or postfusion form in nasal samples Analysis of neutralizing antibodies to Ad26

Objectives	Endpoints
Cohorts 2 and 3	
Primary	

 To assess the safety and reactogenicity of different dose levels of the Ad26.RSV.preF-based vaccine 	
 Solicited local and systemic AEs from the time of vaccination until 7 days after vaccination Unsolicited AEs from the time of vaccination until 28 days after vaccination
Secondary	

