9.4.3. Safety Analyses

No formal statistical testing of safety data is planned. Safety data will be analyzed descriptively by cohort and group. In addition, for a selection of tables, data of Cohorts 2 and 3 may be pooled. All safety analyses will be based on the FAS.

AEs (Solicited and Unsolicited)

Solicited local (injection site) and systemic AEs will be summarized descriptively. Solicited AEs shown in the tables and listings will be based on the overall assessment of the investigator. The overall frequencies per group as well as frequencies according to severity and duration will be calculated for solicited AEs. In addition, the number and percentages of participants with at least one solicited local (at the injection site) or systemic AE will be presented.

The verbatim terms used in the eCRF by the investigator to report AEs will be coded using the Medical Dictionary for Regulatory Activities (MedDRA). All reported AEs with onset during the active vaccination phase (ie, AEs occurring from the time of vaccination until 28 days after vaccination) and all SAEs will be included in the analysis. For each AE, the number and percentage of participants who experience at least one occurrence of the given event will be summarized by group. Frequency tables of unsolicited AEs, separately for all and study vaccine-related, will be presented by system organ class and preferred term.

Summaries, listings, datasets, or participant narratives may be provided, as appropriate, for those participants who die, who discontinue study vaccination due to an AE, or who experience a severe AE or an SAE.

Summaries and/or listings may be provided separately for AEs with onset outside the above defined timeframe (ie, beyond 28 days after vaccination).

Clinical Laboratory Tests (Cohorts 2 and 3 only)

Laboratory abnormalities will be determined according to the FDA toxicity grading tables (Section 10.2, Appendix 2) or, for tests for which no grades are available, in accordance with the normal ranges of the clinical laboratory. Any laboratory value shown as a "graded" value in the FDA table that is within central laboratory normal ranges will not be graded for severity.

Vital Signs

A tabulation of the distribution of body temperatures per half degree intervals will be provided. For systolic and diastolic blood pressure and heart and respiratory rate, the percentage of participants with values beyond clinically relevant limits will be summarized.

Physical Examination

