## 6. SAFETY

Continuous variables will be summarized using the following statistics, as appropriate: number of observations (N), arithmetic mean (mean), 95% confidence interval (CI) for the mean, standard deviation (SD), standard error (SE), median, quartiles (Q1 and Q3), minimum and maximum. Frequencies and percentages (to one decimal place) will be generated for categorical variables.

Safety data will be summarized per cohort, vaccine group and study phase. In addition, for a selection of tables, data of Cohorts 2 and 3 may be pooled over cohorts.

Safety data will be presented only for the active period or phase, except SAEs which will be presented in all phases in which they were reported. The analysis phases are defined in Section 2.1.1. Denominator for the percentages is the number of subjects in the considered analysis set and period/phase for a certain vaccine group (incidence per 100 subjects/period).

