#### 6.1.1. Definitions

The analysis of solicited AEs will be based on the overall assessment by the investigator. For unsolicited AEs, only the AEs starting within the 28-day period following vaccination will be presented in the safety tables, except for SAE, which will be captured and presented throughout the study. Unsolicited non-serious adverse events collected outside the 28-day period following the vaccination will be presented through listings.

By definition, all solicited AEs at the injection site (local) will be considered related to the study vaccine administration.

The severity of the AEs (solicited and unsolicited) will be classified as Mild (Grade 1), Moderate (Grade 2), Severe (grade 3) or Potentially Life Threatening (Grade 4). See CTP Section 10.2 and 10.3 for details on the criteria for the AE severity classification.

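### SAP Table 1 can run the active AE period past the 28 days fixed by the endpoint and SAP 6.1.1, and the Day 29 contact may fall before those 28 days are over

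*SAP*

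**What the plan says.** Four places fix the period at 28 days:

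- **Endpoint** (protocol 3; primary in Cohorts 2 and 3, secondary in Cohort 1): "Unsolicited AEs from the time of vaccination until 28 days after vaccination".
- **Collection rule** (protocol 1.3, footnotes to both schedules): "All other AEs (unsolicited) and other special reporting situations will be reported from the time of vaccination until 28 days after vaccination". The exceptions are AEs related to study procedures or to noninvestigational sponsor products, AEs leading to discontinuation of vaccination, and SAEs.
- **Protocol analysis section** (9.4.3): the analysis covers AEs with onset in the "active vaccination phase (ie, AEs occurring from the time of vaccination until 28 days after vaccination".
- **SAP 6.1.1**: "only the AEs starting within the 28-day period following vaccination will be presented in the safety tables". SAEs are excepted, and later non-serious unsolicited AEs go to listings.

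A second set of SAP rules works by phase:

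- **SAP Table 1, item (c)**: the post-dose period ends at "Maximum (28 days after first vaccination at 23:59, scheduled visit 4 weeks after first vaccination at 23:59", unless last contact after early discontinuation or an interim cut-off comes sooner.
- **SAP 6.1.3, Step 1**: an unsolicited AE belongs to the phase in which it starts.
- **SAP 6**: "Safety data will be presented only for the active period or phase, except SAEs". Percentages use the number of subjects in that period as denominator.

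SAP 1.6 records no change from the planned analysis. Both Schedules of Activities place the contact at 28 days after vaccination (Day 29), ±7 days, by phone or electronic means if wished. The next visit is Day 85 ±14 days. SAP 6.1.4 treats a subject with no reported event as having had none.

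**The concern.** Two separate matters affect the same endpoint.

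**Analysis period.** A programmer who follows Table 1 with SAP 6 and 6.1.3 will tabulate an event starting on study Day 33 if the participant was contacted on Day 36. The same event falls in follow-up if the contact was on Day 29. A programmer who follows SAP 6.1.1 will list it in both cases. The SAP does not say which rule prevails. Under the first, the content of a 28-day table depends on when each participant happened to be contacted, and the added days are ones in which non-serious AEs are mostly no longer collected.

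**Ascertainment.** The Day 29 contact is the only scheduled enquiry between the Day 15 and Day 85 visits. If it takes place early, the last days of the 28-day period depend on the participant reporting unprompted, or on recall many weeks later. Because silence counts as no event, any error is towards under-counting.

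**Working it through.** **Inputs.** Study-day convention from SAP 2.1: "Study Day = visit date – date of Day 1 + 1" for dates on or after vaccination, so study day = days after vaccination + 1. Visit timings and windows come from protocol 1.3.1 and 1.3.2. The end of the period comes from SAP Table 1, item (c).

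**Step 1: reproduce the SAP's own windows.**

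- Day 15, −3/+7: 15 − 3 = 12 and 15 + 7 = 22, giving [12, 22].
- Day 85, ±14: 85 − 14 = 71 and 85 + 14 = 99, giving [71, 99].
- Day 183, ±14: 183 − 14 = 169 and 183 + 14 = 197, giving [169, 197].

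All three agree with SAP Table 2.

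**Step 2: Day 29 contact, ±7.** 29 − 7 = 22 and 29 + 7 = 36, so study Days 22 to 36, or 21 to 35 days after vaccination.

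**Step 3: Table 1, item (c), for a participant who does not discontinue.** With the visit term read as the actual contact date, end of period = max(28, days from vaccination to contact).

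| Contact, days after vaccination | End of post-dose period, days after vaccination | Study day of end |
|---|---|---|
| 21 | max(28, 21) = 28 | 29 |
| 28 | max(28, 28) = 28 | 29 |
| 31 | max(28, 31) = 31 | 32 |
| 35 | max(28, 35) = 35 | 36 |

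The extension within the window is at most 35 − 28 = 7 days. Item (c) has no cap at the window's edge, so a later contact would extend it further. An early contact never shortens the period.

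**Step 4: the other reading of the visit term.** If *scheduled visit* means the nominal date, 4 weeks = 28 days and the expression is max(28, 28) = 28 for everyone. There is then no extension, but the maximum does nothing.

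**Step 5: gap after an early contact.** With a contact on Day 22, Days 23 to 29 (29 − 22 = 7 days) have no scheduled enquiry until the Day 85 visit. From Day 29 that is 71 − 29 = 42 to 99 − 29 = 70 days.

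**Step 6: outer bound on the extension (assumption, not in the documents).** Suppose a constant hazard, complete ascertainment to 35 days and every contact on Day 36. Then risk at 35 days = 1 − (1 − r)^(35/28), where r is the 28-day risk. For r = 5%, 10%, 20% and 30% this gives 6.2%, 12.3%, 24.3% and 36.0%. These are not forecasts: the collection rule does not require most non-serious events after 28 days, and contacts will not all fall on Day 36.

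**The case against.** The strongest reply is that SAP 6.1.1 is the specific rule for the unsolicited-AE tables, agrees with protocol 9.4.3 and should override the general phase rule. If so, nothing beyond 28 days is tabulated. That stands in part: a reader might infer that Table 1 has redefined the endpoint, and the documents do not support this. What they show is a conflict with no stated order of precedence.

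The extension also has little to act on. Beyond 28 days only the excepted categories, and events a participant volunteers at a late contact, could enter the tables; SAEs are presented in all phases anyway. This stands. A reader might take the 7 extra days on 28 (7/28 = 25%) as a 25% change in incidence. It is calendar time only, and the denominators are subjects, not person-time.

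A reader might also infer that a Day 22 contact ends AE collection a week early. No section says so. Collection runs to 28 days by rule, the schedules mark it as continuous, participants must be able to reach the investigator and they carry a card with a 24-hour number. The maximum in Table 1 also keeps the analysis period at 28 days. What remains is the lack of a scheduled prompt for the last days.

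Finally, allocation within each cohort is randomized and double-blind, nothing suggests that contact timing differs by group, and no formal testing is planned. This argues against bias between groups. It does not remove possible under-counting of the incidences themselves.

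**Conclusion.** The point holds as an inconsistency in the SAP and a gap in ascertainment. Table 1 item (c), applied through SAP 6 and 6.1.3, contradicts SAP 6.1.1, protocol 9.4.3 and the endpoint. It can carry the active period to 35 days after vaccination for an in-window contact. This rests on reading the visit term as the actual date, which is the only reading that gives the maximum a purpose. The effect on reported incidence is probably small and cannot be estimated from the documents.

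The ±7-day window can leave up to 7 days of the 28 without a scheduled enquiry for a further 42 to 70 days. For participants enrolled last, that enquiry may come after the primary analysis that is meant to contain 28-day safety data; the documents give no cut-off date that would settle this. Under-ascertainment is possible, and its size depends on the unknown share of early contacts and on how many events go unreported. No sample-size figure is affected. The changes should be made because they are cheap and concern a primary endpoint in Cohorts 2 and 3.

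**What to change.** 1. **SAP Table 1, item (c):** delete the visit term, so that the post-dose period ends at 23:59 on the day 28 days after vaccination (study Day 29), subject to the existing limits for early discontinuation and interim cut-off. Table 1, SAP 6, 6.1.1 and 6.1.3 then agree with protocol 9.4.3. This is a one-line SAP edit; a few events may move from tables to listings.

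2. **Protocol 1.3.1 and 1.3.2:** ensure an AE enquiry at or after 28 days. Either change the Day 29 window to 0/+7 days, or keep ±7 days and add a short phone or electronic contact whenever the first one occurs before 28 days have passed. The Day 15 visit already has an asymmetric window.

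The cost of the second change is a narrower window or an occasional extra call. The window change needs a protocol amendment, with ethics committee approval before use unless it counts as purely logistic or administrative under protocol 10.4.
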